## 1 PROTOCOL SUMMARY

### 1.1 Synopsis

**A+ Treatment:** Feasibility trial of adapted ESDM-informed caregiver coaching delivered remotely for children with Autism Spectrum Disorder (ASD) and Attention-Deficit/Hyperactivity Disorder (ADHD); Duke Autism Center of Excellence (Duke ACE), Project 3; Protocol Pro00085179, v1.0 23 October 2020)

**Study Description:** This study will evaluate the feasibility of adapted ESDM-informed caregiver coaching in children with comorbid ASD and ADHD, who are between 36 and <132 months of age. There will be no study provided medication treatment in this study. Children will either be on ADHD medication prescribed by their own personal provider or will not be taking any ADHD medication (this will be documented by the study). The provided behavioral treatment will be eight ~60-minute sessions in ESDM-informed caregiver coaching remotely delivered weekly, for 8 consecutive weeks. The behavioral treatment is provided to children through Early Start Denver Model (ESDM)-informed caregiver coaching strategies, implemented within the child's typical daily routine by the caregiver. Pre-baseline procedures included screening and eligibility procedures, cognitive & diagnostic assessments. This was followed by baseline visit (Week 0), 8 subsequent weekly coaching sessions (Weeks 1 - 8), an endpoint visit (Week 9), and a follow up visit (Week 16).

**Objectives:** The overarching goal of A+ Treatment is to evaluate feasibility and gather

pilot data of remotely-delivered ESDM informed caregiver coaching for children with ASD and ADHD which may inform future combination clinical trials (pharmacotherapy and behavioral intervention).

**Primary Endpoint:** Using an implementation science approach we will characterize the acceptability, appropriateness, feasibility and fidelity of remotely behavioral intervention in the following ways: 1. Using 3 pragmatic measures: Acceptability of Intervention Measure (AIM), Intervention Appropriateness Measure (IAM), and Feasibility of Intervention Measure (FIM). 2. Conducting qualitative interviews (caregiver, clinician and staff) of perceptions regarding the intervention. 3. Assessing fidelity of intervention delivery, using adapted ESDM Fidelity rating scales.

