communication, imitation, joint attention, speech development, functional and symbolic play skills, and management of challenging behavior in the context of parent identified social communication goals. The first study of P-ESDM evaluated the benefits of 1 hour/week of parent-coaching for 12 weeks in 8 children with ASD. Parents acquired the strategies and achieved fidelity by the 6th week(23). Children demonstrated sustained increases in joint attention, social engagement, social initiation, imitation and functional communicative behaviors (Figure 2).

Next, a larger (N = 98), NIH-funded RCT was conducted, evaluating the same brief 12-week, 1 hour/week of P-ESDM parent coaching vs. treatment-as-usual (TAU) in the community(21). The TAU group received significantly more hours of intervention, many of which were delivered by trained professionals. Both groups demonstrated similar statistically significant improvements in social symptoms and communication abilities, as measured by the ADOS social affect score and the Mullen Scales of Early Learning respectively. Parents in the P-ESDM group demonstrated significantly lower levels of parenting stress. A+ Treatment will utilize principles derived from P-ESDM for 8 caregiver coaching sessions.

Zhou et al. (24) evaluated the effects of a more intense version of P-ESDM that provided 1.5 hours/week of parent coaching for 6 months vs. treatment-as-usual in the community. The control group was comprised of children with ASD who did not live near the university where the study was being conducted, and, thus, could not feasibly attend weekly treatment. At baseline, there were no group differences in gender, birth history, parental education and income, parental age, or number of siblings. With appropriate controls for baseline scores and intervention hours received, the P-ESDM group showed significantly greater improvements on the Griffiths Mental Development Scales T-scores in the Social (M = 5.4 vs. -4.4; p = 0.001) and Receptive/Expressive Language (M = 20.3 vs. -6.6; p < 0.001) domains.

Research on the developmental impact of the intervention after parent coaching is relatively more limited, although the impact of therapist delivered ESDM is typically assessed after 1-2 years and benefits appear to increase over time.

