### 2.3 Specific Aims

Approximately half of children with autism spectrum disorder (ASD) have co-occurring attention deficit hyperactivity disorder (ADHD) (11, 12). Unfortunately, the long-term outcomes of individuals with comorbid ASD and ADHD (ASD+ADHD) are significantly worse than individuals with ASD or ADHD. Those with ASD+ADHD are often diagnosed with ASD significantly later and exhibit more behavioral problems, poorer peer relationships and increased use of restricted educational settings (13-15). We suspect these negative outcomes in individuals with ASD+ADHD are, in part, the consequence of ADHD symptoms compromising the individual's ability to fully benefit from behavioral interventions for ASD, which all require the interventionist to acquire and sustain the child's attention. Thus, we hypothesize that we can intervene to reduce negative outcomes in children with ASD+ADHD by concurrently providing ADHD treatment and ASD treatment.

The overall purpose of this project is inform the most feasible design of a future clinical trial combining ADHD treatment with ASD behavioral treatment in children with ASD+ADHD to test our hypotheses. To do this, we are evaluating the feasibility of various trial designs. This sub study will be delivered completely remotely and will allow participants and their families to choose whether to treat ADHD symptoms or not in consultation with community providers.

**Aim 1. Assess implementation outcomes.** Assess acceptability, appropriateness, feasibility, and fidelity of remotely delivered ESDM-informed caregiver coaching intervention which has been adapted for older children who have comorbid ADHD for delivery over a period of 8 weeks. Acceptability, appropriateness, and feasibility will be quantitatively and qualitatively assessed using 4-item, pragmatic scales and individual stakeholder interviews. Fidelity of intervention delivery, the degree to which programs are implemented as intended by program developers, is also an important implementation outcome. This will be monitored using an adapted version of the Parent Early Start Denver Model (P-ESDM) Caregiver Fidelity Rating System.

Hypothesis: we will be able to determine acceptability, appropriateness, feasibility, and fidelity by gathering this outcome data through selected endpoints.

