### 5.5 Strategies for Recruitment and Retention

The target sample size is 30-35. We anticipate that 20% or less of the sample will be female due to the lower prevalence of both ASD and ADHD among females. We expect that Caucasians will be modestly overrepresented in the sample due to increased historical comfort with clinical trials than minorities. Further, among minorities we anticipate that Hispanic individuals will be most underrepresented in the sample due to requirements that the parent participating in ESDM-informed caregiver coaching be fluent in English. We expect to enroll 1-3 participants per month.

Participants will be recruited from A+ Assessment, A+ Health, A+ Development, community advertisements, medical records, and physician contacts. Recruitment strategies include: developing radio and newspaper ads and brochures, using social media, attending community events, delivering community talks, meeting with various agencies who provide clinical and educational services for children, developing and maintaining active relationships with local autism and ADHD advocacy and support groups, and reaching out to community pediatricians, family practice doctors, child psychiatrists and psychologists, early intervention programs, and schools to make them aware of the treatment needs of children with ASD+ADHD and the availability of A+ Treatment. We will also approach churches and cultural institutions that serve primarily African American, Hispanic and/or Asian populations about giving informational talks and providing informational materials to increase minority recruitment.

**Retention:** A+ Treatment staff including behavioral therapists will maintain regular ongoing contact with all participants and their families to facilitate retention and discuss any concerns that may arise. We anticipate that any concerns will be adequately addressed during the weekly ESDM-informed caregiver coaching visits. If necessary, some parts of the diagnostic and major assessment visits can be split into 2 visits up to one week apart if the family prefers. In addition, the recruitment core may send birthday/holiday cards, distribute newsletters, and e-blasts; provide diagnostic reports that summarize testing results; provide clinical referrals; and give regular updates about Duke ACE Center and DCABD research and activities.

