## 8 STUDY ASSESSMENTS AND PROCEDURES

- **Acceptability of Intervention Measure (AIM), Intervention Appropriateness Measure (IAM), and Feasibility of Intervention Measure (FIM).** (Weiner et al., 2017) These measures have been administered to a wide range of stakeholders to determine the extent to which they believe an intervention or implementation strategy is acceptable, appropriate, and feasible. Readability is at the 5th grade level. Higher scores indicate greater acceptability, appropriateness, and feasibility. The

AIM, IAM, and FIM have demonstrated content validity, discriminant content validity, reliability, structural validity, structural invariance, known-groups validity, and responsiveness to change. This measure will be completed with participants who enroll in the study, as well as coaches, clinicians, and support staff who consent to conduct the Qualitative Interview and AIM-IAM-FIM survey.

- **Two Early Start Denver Model (ESDM) fidelity scales will be utilized in this study:** (1) ESDM Coaching Fidelity Rating System; and the (2) Parent Early Start Denver Model (P-ESDM) Caregiver Fidelity Rating System. The ESDM Coaching Fidelity Rating System evaluates 14 coaching behaviors during the caregiver coaching sessions. Items are individually rated with a Likert-type rating scale with values that vary from 1 to 4, with higher scores reflecting a greater degree of fidelity. A portion of the items evaluate specific activities within the intervention session (e.g., warm-up activity, coaching on the topic) and the remaining items assess coaching characteristics which are evaluated across the entire session (e.g., reflective, nonjudgmental). The P-ESDM Caregiver Fidelity Scale provides a method for assessing the fidelity with which a caregiver is using ESDM principles in a joint activity routine with their young child. The 13 item rating scale includes ratings of performance from 1 to 3.

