Fidelity of intervention delivery, the degree to which programs are implemented as intended by program developers, is an important implementation outcome because it can moderate the effect of an intervention on targeted health outcomes. When interventions are adapted to fit a new target population, delivery setting, location or organization, maintaining intervention fidelity is of particular importance. Fidelity of caregiver implementation of ESDM strategies will be assessed quantitatively, using an adapted version of the Parent Early Start Denver Model (P-ESDM) Caregiver Fidelity Rating System. The P-ESDM Caregiver Fidelity Scale provides a method for assessing the fidelity with which a caregiver is using ESDM principles in a joint activity routine with their young child. The 13 item rating scale includes ratings of performance from 1 to 5. Observations will be coded from video-recorded caregiver-child interactions completed at baseline (pre-intervention) and at 9-weeks (post-intervention), by certified ESDM therapists who are naïve with respect to whether they are coding the baseline or 9-week observation. Tabular and graphical summaries of pre and post caregiver implementation fidelity will be generated to assess the degree to which the average in the cohort changes over time. Inference on pre-post change will be based on paired t-tests or, if the assumptions are found to be untenable, the Wilcoxon signed rank test for paired samples.

---

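### Caregiver fidelity is defined as a level of implementation, but the plan tests only change in its average and sets no standard for the week-9 level

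*Combined protocol and SAP*

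**What the plan says.** The Synopsis (1.1) lists fidelity within the primary endpoint: "Assessing fidelity of intervention delivery, using adapted ESDM Fidelity rating scales". Section 3 does the same. Aim 1 in section 2.3, and again section 9.3.2, define fidelity as "the degree to which programs are implemented as intended by program developers".

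For caregivers, section 9.3.2 plans ratings of baseline and week-9 videos by certified therapists who do not know which time point they are coding. Tables and graphs of pre and post "caregiver implementation fidelity will be generated to assess the degree to which the average in the cohort changes over time". The inference follows: "Inference on pre-post change will be based on paired t-tests", with the Wilcoxon signed rank test as fallback. Section 9.3.3 uses almost the same wording for the Aim 2 outcomes, where change is the stated question.

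No section gives a fidelity cut-off, a target week-9 level, or a count of caregivers who reach one.

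The item range is given in two ways for the same 13-item scale. Section 8 has "The 13 item rating scale includes ratings of performance from 1 to 3"; section 9.3.2 has "The 13 item rating scale includes ratings of performance from 1 to 5". Section 6.1.3 also uses 1 to 3 for the therapist's in-session rating of caregivers.

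Coach fidelity is collected too: 14 items rated 1 to 4 (section 8), from one randomly chosen session video per participant, scored by an independent rater (section 6.1.3). Section 9 gives no analysis of it.

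**The concern.** Implementing a programme as intended is a matter of how close caregivers come to a standard. A paired test has no change as its null hypothesis, so it answers a different question: whether scores moved between baseline and week 9. The two answers can come apart in both directions. A small rise can be significant while most caregivers remain short of any reasonable standard. A cohort that starts high can stay high and give a null result.

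The trial's purpose is to inform the design of a later combination trial. Section 9.3.2 itself stresses that fidelity matters particularly when an intervention is adapted to a new population or setting. Here the coaching is remote, in 8 sessions, for older children with ADHD. The designer of the next trial will want to know whether caregivers use the strategies adequately by week 9. The background treats fidelity in this way when it describes the first, 8-child study of the parent-delivered programme: "Parents acquired the strategies and achieved fidelity by the 6th week". The planned inference cannot give an answer of that kind.

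**Working it through.** **No figure to reproduce.** The plan states no alpha, SD, effect size, power or cut-off for fidelity. Section 9.1 bases the sample size on expected recruitment.

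**Inputs from the plan**
- Section 5.5: "The target sample size is 30-35"; section 5 gives 35.
- Section 5.5: attrition of about 15%. 30 × 0.85 = 25.5 and 35 × 0.85 = 29.75, so about 25 to 29 pairs, and 35 with no loss.

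**Assumptions (not in the plan)**
- Two-sided alpha of 0.05.
- SD of change of 0.3 to 0.8 points per item.
- Between-caregiver SD of 0.5 to 0.8 on a 1–5 scale, or 0.3 on a 1–3 scale.
- An illustrative cut-off at 80% of the scale maximum (4.0 or 2.4). This serves only to show the arithmetic; the documents give no source for it.

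**Step 1. Smallest significant mean change.** In SD-of-change units this is t(0.975, n−1)/√n.
- n = 25: 2.064/5 = 0.413
- n = 29: 2.048/√29 = 0.380
- n = 30: 2.045/√30 = 0.373
- n = 35: 2.032/√35 = 0.344

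**Step 2. The same in points per item.** With an SD of change of 0.5, the values for n = 25, 29 and 35 are 0.21, 0.19 and 0.17. Over SDs of 0.3 to 0.8 the range runs from 0.344 × 0.3 = 0.10 to 0.413 × 0.8 = 0.33.

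**Step 3. What a just-significant rise can coexist with.** The share at or above the cut-off is 1 − Φ((cut-off − week-9 mean)/between-caregiver SD), for n = 25 to 35.

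| Scale | Assumed baseline mean | Week-9 mean | Share at or above cut-off |
|---|---|---|---|
| 1–5, SD of change 0.5 | 2.5 | about 2.7 | 0.4% to 5% |
| 1–5, SD of change 0.5 | 3.0 | about 3.2 | 5% to 16% |
| 1–3, both SDs 0.3 | 1.5 | about 1.6 | 0.4% to 0.5% |

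These shares depend heavily on the assumed baseline and cut-off. They show that a significant rise and low attainment are compatible, not that this is the likely result.

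**Step 4. Precision of an attainment proportion.** Exact (Clopper-Pearson) 95% intervals:
- 20/25 (80%): 59% to 93%
- 23/29 (79%): 60% to 92%
- 28/35 (80%): 63% to 92%
- 12/25 (48%): 28% to 69%

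The intervals are wide, but they address the level that the definition refers to.

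**The case against.** The best defence is that this is a descriptive pilot. No primary outcome has a pass/fail rule, Aim 1's hypothesis is only that fidelity can be determined from the data, and section 9.3.2 centres the primary feasibility analysis on the AIM, IAM and FIM. A reader might infer that a small rise would let fidelity pass. The documents do not support that, because there is nothing to pass; the risk is one of interpretation.

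The plan also summarises both time points, so the week-9 level will be visible. Section 9.3.3 offers boxplots as an example for very similar wording, and such plots could reveal a split between caregivers who progressed and those who did not. It would be too strong to say that the plan hides the level or any split. What is missing is a standard for reading it and a commitment to count who reaches it.

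Two further readings are tempting. One is that the plan dropped an attainment measure used in earlier work. Nothing shows that it ever had one, and the cited study's criterion is not in the documents. The other is that caregivers are untrained at baseline, so that the test only asks whether they learned anything. The documents do not say so: section 5.2 does not exclude prior training, and intervention history is collected.

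Section 9.3.1 promises a final SAP before database lock, where a criterion could still appear. That is a place for the change; it does not supply a criterion in the current text. Finally, any paired test can detect a modest shift, so the figures do not reveal a flaw peculiar to this trial. They show why its result cannot stand in for a statement about level.

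**Conclusion.** The point holds as a mismatch between a primary construct and its analysis. Fidelity is defined as a level, the only inference concerns change in the mean, and no section supplies a standard for week 9. The threshold of 0.34 to 0.41 SD of change rests only on two-sided alpha of 0.05 and 25 to 35 pairs. Any translation into scale points or shares of caregivers rests on the assumed SDs, baselines and cut-off above.

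The blinded ratings are suitable for answering the right question, so the weakness lies in how they will be summarised and read. Two related gaps belong with it: the contradictory item range, which must be settled before any cut-off has meaning, and the absence of an analysis for coach fidelity, which is the more direct measure of delivery.

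**What to change.** 1. Reconcile the item range of the caregiver fidelity scale across sections 6.1.3, 8 and 9.3.2.
2. In the final SAP, before database lock and before the fidelity scores are analysed, name the criterion for week-9 caregiver fidelity. Use the adapted scale's own criterion, or a justified one set by the sponsor if it has none. The Summary of Changes shows that participants had already reached week 16 by August 2021, so requiring this before any video is coded may no longer be possible.
3. In section 9.3.2, report the week-9 mean with its 95% confidence interval. Report the number and percentage of caregivers at or above the criterion at baseline and at week 9, with exact 95% intervals and stated denominators.
4. Base the fidelity conclusion on the week-9 level and keep the paired change test as supportive.
5. Add a descriptive summary of the coach fidelity ratings.

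The cost is protocol and SAP wording; no new data or participants are needed. The downsides are that the criterion must be fixed and defended in advance, that the proportion will be imprecise at this sample size, and that it may look less favourable than a significant mean change.

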### 9.3.3 Analysis of the secondary endpoints

Proximal child and caregiver outcomes. A key proximal outcome will be change from baseline (pre-intervention) to 9-weeks (immediately post-intervention) in caregiver ) sense of competence measured by the Parent Sense of Competence Scale and child behaviors measured by the sum of 4 items from the JERI (Joint Engagement, Attention to Caregiver, Responsiveness to Partner’s Communication Bids, Fluency and Connectedness) coded by a trained, reliable coder who is naïve with respect to whether the observation is from baseline our outcome using video-recorded caregiver-child interactions.

Aim 2 data analysis: Quantitative measures, including participant demographics, will be summarized using descriptive statistics. Means and standard deviations will be reported for continuous measures, and frequency and percentages are reported for categorical variables. Tabular and graphical summaries of each outcome measure at each assessment point will be generated to assess the degree to which the average in the cohort changes over time (e.g. boxplots of VABS-3 Communication at baseline and follow up). Inference on pre-post change will be based on paired t-tests or, if the assumptions are found to be untenable, the Wilcoxon signed rank test.

---

### 9.3.4 Safety analyses

There is no study provided medication in this sub-study. However, AEs will be collected. Each AE will be counted once only for a given participant. TEAEs will be presented by severity.

---

### 9.3.5 Baseline descriptive statistics

Baseline descriptive statistics will include demographics, ADOS/BOSA severity scores, cognitive function, adaptive behavior scores, ADHD-RS scores using descriptive statistics of mean value, standard deviation and range.

---

### 9.3.6 Planned interim analyses

No interim analyses are planned.

---

### 9.3.7 Sub-group analyses

If subgroup analyses are done, they will be purely non-inferential and hypotheses generating, given that this is a pilot study with a small sample size that is unlikely to have subgroups of sufficient size to draw meaningful conclusions.

---

### 9.3.8 Exploratory analyses

Additional Exploratory proximal and distal outcomes of interest include: a) caregiver ADHD-RS ratings of the child’s attention. b) Aberrant Behavior Checklist (ABC), including inattention/hyperactivity, social withdrawal, stereotypies, irritability, and inappropriate speech; c) Social Reciprocity Scale-2 (SRS-2) ratings of child’s social communication behavior; d) Caregiver Strain Questionnaire (CSQ) ratings of the impact of the child’s condition on the family and caregiver and quality-of-life; e) Behavior Rating Inventory of Executive Functions (BRIEF) ratings of child’s executive function; and f) Child Behavior

Checklist (CBCL) ratings of child behavioral and emotional problems. Our analysis will focus on graphical displays, which will be complemented by appropriate inferential statistical procedures. For the graphical displays, we will visualize the distribution of proximal and distal outcome measures in histograms to better understand the shape and spread of the distribution of each. In terms of inference, between group change at proximal and distal time points will be based on between group t-tests or, if the assumptions are found to be untenable, the Mann-Whitney U test. Whilst statistical inference is valuable, we anticipate that we will elicit most information through careful data visualization. Change from baseline (pre-intervention) to 16-weeks (8-weeks post-intervention) will be assessed for the VABS-3 Socialization and Communication Subscale Standard Scores.

